At the initial visit eligibility will be confirmed and informed consent will be gained for all activities in the trial. The nature and objectives of the study will be explained, and potential risks discussed. This information will be presented in a written patient information sheet (PIS) sent to potential participants prior to the in person visit, giving participants time to consider their participation. The process for withdrawal, including the subsequent impact on data and sample storage will be described.

At this point capacity to consent to be in the trial will be assessed. Participants will then sign a written consent form, and a copy of the information sheet and consent form given to them, and other copies stored in the trial file.

	Assessment periods	
Visits	1 (Baseline, in person)	V2 (Week 12, in person)
Time per session	Max 2 hr	Max 1 hr
Day	0	84
Medical history, incl. Concomitant medication	Х	
Assessment of inclusion/exclusion criteria	Х	
Informed consent	X	
SPPB	х	х

Qol questionnaire (also to be filled in at wk 4, 8)	х	х
7 day food intake questionnaire*	X	x
Blood	X	x
Saliva	X	X
Vital signs/bmi	Х	х
Adverse event reporting		Х
Capsule distribution	X	
Compliancy pill count		х

^{*}Food diary to be returned at V2

Data Protection and Confidentiality

All laboratory specimens and case record forms will be identified in a manner designed to maintain participant confidentiality. Laboratory specimens will arrive at the lab in a pseudo anonymised form. The anonymisation will be done by the person taking the sample. All records will be kept in a secure storage area in the Institute of Inflammation and Ageing with limited access to study staff only. Information will not be released without the written permission of the participant, except as necessary for monitoring and auditing by the Sponsor, its designee or Regulatory Authorities. The CI and study staff involved with this study will not disclose or use for any purpose other than performance of the study, any data, record, or other unpublished, confidential information disclosed to those individuals for the purpose of the study.

The CI and study staff involved with this study will comply with the requirements of the Data Protection Act 2018 with regard to the collection, storage, processing and disclosure of personal information and will uphold the Act's core principles. Access to collated participant data will be restricted to the CI and appropriate study staff.

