Computers used to collate the data will have limited access measures via user names and passwords.

Published results will not contain any personal data that could allow identification of individual participants.

GP Notification

We will inform he GP of the participants involvement in the study if the participant consents to this

Safety reporting

An adverse event (AE) is any untoward medical event affecting a clinical trial participant. Each initial AE will be considered for severity, causality or expectedness and may be reclassified as a serious event or reaction based on prevailing circumstances.

An adverse reaction (AR) is where it is suspected that an AE has been caused by a reaction to the trial supplement

A serious adverse event (SAE), serious adverse reaction (SAR) or suspected unexpected serious adverse reaction (SUSAR) is any AE, AR or UAR that at any dose:

- results in death
- is life threatening
- requires hospitalisation or prolongation of existing hospitalisation
- results in persistent or significant disability or incapacity
- is a congenital anomaly or birth defect
- Or is otherwise considered serious

Note: Hospitalisations for treatment planned prior to consent and hospitalisation for elective treatment of a pre-existing condition will not be considered as an SAE. However any adverse events occurring during such hospitalisation will be recorded. Adverse events, adverse reactions and serious adverse events will be reported by participants or other health care professionals.

A telephone contact will be made at 4 and 8 weeks to ensure no adverse events are missed.

All AEs and SAEs will be recorded from the time a participant consents to join the study until the last study visit. Participants with unresolved AEs at the last study visit will be followed up until resolution or 30 days after last visit of that participant, whichever is sooner. SUSARS will be followed until resolution.

The CI, or delegate will ask about the occurrence of AEs and hospitalisations at every telephone check (week 4 and 8) and at the second/final study visit (week 12). AEs will be recorded on the AE Log in the CRF. SAEs will be submitted on an SAE form to the Sponsor within 24 hours of becoming aware of the SAE. SAEs will be assessed for expectedness and causality by the Investigator. The evaluation of expectedness will be made based on the knowledge of the reaction and the relevant product information.

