This study is funded by a research grant from Bayer Healthcare Pharmaceuticals

Peer review

This protocol has undergone both internal (within the Institute of Inflammation and Ageing) and external peer review

Protocol Deviations and Breaches

The CI will not implement any deviation from the protocol without agreement from the Sponsor, except where necessary to eliminate an immediate risk to trial participants.

In the event that the CI needs to deviate from the protocol, the nature of and reasons for the deviation will be recorded in the CRF, documented and notified to the Sponsor. If this necessitates a subsequent protocol amendment, this will be submitted to the Sponsor for approval and then to the appropriate REC, Regulatory Authority and local NHS R&D for review and approvals as appropriate.

In the event that a serious breach of the protocol or GCP is suspected, this will be reported to the Sponsor immediately.

End of Study and Archiving

The end of study is defined as last patient last visit. The Sponsor and CI have the right at any time to terminate the study for clinical or administrative reasons.

The end of the study will be reported to the Sponsor, REC, Regulatory Authority and NHS R&D Office(s) within 90 days, or 15 days if the study is terminated prematurely.

Archiving of study documents will be carried out as specified in UoB-ARC-SOP-001 Standard operating Procedure: Archiving . All study documentation will be kept for 110years.

Access to the final data set

The final data set will be available on request to the CI

Dissemination plans

The clinical study report will be used for publication and presentation at scientific meetings.

Summaries of results will also be made available to Investigators for dissemination within their clinical areas (where appropriate and according to their discretion).

Authorship Eligibility Guidelines

Ownership of the data arising from this study resides with the study team and their respective employers. On completion of the study, the study data will be analysed and tabulated, and a clinical study report will be prepared.

Authorship eligibility for each manuscript arising from this study will be determined according to the criteria laid out in the Working Practice Document on Authorship filed in the Study Operations Manual.

We have no plans to use professional writers

References

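### Only SUSARs are followed to resolution, so any other serious event still open 30 days after the last visit leaves planned follow-up with no final outcome

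*Protocol*

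**What the plan says.** All the rules on event follow-up are in the Safety reporting section of the protocol.

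- **Definitions.** "An adverse event (AE) is any untoward medical event affecting a clinical trial participant". An SAE, SAR or SUSAR "is any AE, AR or UAR that at any dose" meets one of the listed seriousness criteria.
- **Recording.** "All AEs and SAEs will be recorded from the time a participant consents to join the study until the last study visit".
- **Follow-up.** Participants whose AEs are unresolved at the last visit are "followed up until resolution or 30 days after last visit of that participant, whichever is sooner. SUSARS will be followed until resolution". The second of these sentences exempts SUSARs from the limit. No other class is exempted.
- **Reclassification.** An AE "may be reclassified as a serious event or reaction based on prevailing circumstances". No time limit is given.
- **Notification and assessment.** Every SAE goes to the sponsor within 24 hours of awareness, and the investigator assesses its causality and expectedness.

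The End of Study and Archiving section adds: "The end of study is defined as last patient last visit".

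**The concern.** A serious event gets open-ended follow-up only if it is judged to be caused by the supplement and also unexpected. Those two judgements properly decide how fast an event is reported onward. They do not decide whether its outcome is worth knowing, which depends on how serious it is. Persistent disability or incapacity is one of the protocol's own seriousness criteria. An event of that kind could well be unresolved at the cut-off, yet it is capped unless it is classed as a SUSAR.

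The causality judgement is also hard to make here. There is no control group, and the Ethical and regulatory considerations section states in advance that the product is not expected to present risks. A serious event judged unrelated is therefore the realistic case for the cap. What is at stake is the completeness of the outcome record for the few serious events that a trial of 85 people may see. Detection is not at stake.

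**Working it through.** The protocol states no figure to reproduce. The check consists of reading the rules together, working out the follow-up window, and putting bounds on the number affected.

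**1. Does the cap cover serious events?** An AE is any untoward event, and an SAE or SAR is an AE or AR that meets a seriousness criterion. Serious events are thus a subset of AEs and fall under the follow-up sentence. There is one ambiguity: the recording sentence names AEs and SAEs, while the follow-up sentence names AEs only. If SAEs are read as lying outside the follow-up sentence, their follow-up is not specified at all. Neither reading takes a non-SUSAR serious event to resolution.

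**2. Classes side by side, if unresolved at the last visit.**

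| Event | Planned follow-up |
|---|---|
| Non-serious AE | at most 30 days after last visit |
| SAE judged unrelated | at most 30 days after last visit |
| Serious reaction judged expected | at most 30 days after last visit |
| SUSAR | to resolution, no limit |

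**3. Length of the window.** The visit table puts the last visit at day 84. The cut-off is day 84 + 30 = day 114. An event starting on day d can be followed for up to 114 − d days:

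- onset at day 0: 114 days
- onset at day 84: 114 − 84 = 30 days

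**4. Reclassification.** It can happen at any time up to the cut-off, and an SAE re-judged as a SUSAR would then be followed to resolution. After the cut-off no further contact is planned for a capped event, so nothing is scheduled that would bring new information.

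**5. How many participants.** The documents give no SAE rate. Assuming that 1%, 2% or 5% of 85 participants have an SAE:

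- 85 × 0.01 = 0.85
- 85 × 0.02 = 1.7
- 85 × 0.05 = 4.25

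These counts cover all SAEs and so are upper bounds. The rule affects only those that are not SUSARs and are also unresolved at the cut-off. At the 1% and 2% rates the expected number affected is below two even if every SAE met both conditions. At 5%, reaching two would need 2 / 4.25 = 47% of SAEs to meet both. Zero to two is therefore a reasonable working range, and zero is quite possible.

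**6. End of study.** The study ends at the last participant's last visit, but follow-up of that participant's open events may run up to 30 days longer, or without limit for a SUSAR. This activity is planned after the defined end of study.

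**The case against.** The case for leaving the rule alone has several good parts.

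- **Reclassification is provided for.** A reader might infer that an event first judged unrelated can never be reclassified. The text does not support that: the provision has no time limit, and an event can be re-judged throughout follow-up. Only the planned flow of new information stops.
- **Most events are untouched.** A reader might also infer that every non-SUSAR serious event is abandoned at 30 days. That is wrong on two counts. Events that resolve earlier have their outcome, and the clock runs from the last visit and not from onset.
- **Expected serious reactions are unlikely.** The risk table lists only minor effects at trial doses and interactions at doses far above them. On that text a suspected serious reaction would ordinarily be unexpected, and so would be a SUSAR. Appendix 1 is not available to settle this.
- **Other safeguards exist.** All SAEs reach the sponsor within 24 hours, and AEs are asked about at weeks 4, 8 and 12. Participants are healthy and non-frail, and safety is not a stated objective.
- **The end-of-study definition cancels nothing.** Follow-up past the last visit is required explicitly. The 30-day tail fits within the 90-day end-of-study notification and the one-year final report.

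All of this stands, and it narrows the point. It does not remove it. An SAE judged unrelated and still open at the cut-off has no planned outcome collection, and nothing in the protocol explains why outcome collection should turn on the causality judgement.

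**Conclusion.** The point holds in a limited form. As written, only SUSARs are followed to resolution. Any other serious event, in practice mainly an SAE judged unrelated, leaves planned follow-up if it is unresolved 30 days after the participant's last visit. Its final outcome is then not recorded.

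The effect is small in number, probably zero to two participants. That range rests on assumed SAE rates of 1% to 5% and on the judgement that well under all SAEs would be both non-SUSAR and still open. It still deserves a change, because in a trial of this size one serious event without a known outcome is a visible gap in the safety record.

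The mismatch with the end-of-study definition is a minor matter of consistency. A reader might infer that the definition cuts off follow-up or loses data, but the documents show neither.

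**What to change.** In Safety reporting, confine the 30-day limit to non-serious AEs. State that all SAEs, SARs and SUSARs are followed until resolved or stable, with the outcome recorded. Outcome collection then depends on seriousness. Adding stability as an end point also gives a workable stop for a SUSAR that never resolves, which the present sentence lacks. This changes the collection of safety data only and does not touch treatment.

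In End of Study and Archiving, reconcile the definition with the follow-up scheduled after the last visit. Either extend the end of study to completion of safety follow-up, or state that such follow-up continues after it.

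The cost is a few sentences of amendment, a few extra telephone contacts for probably no more than one or two participants, and possibly a later close-out of the safety data.
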